13.1.8 MRI

The imaging specialist at the study site's MRI facility is responsible for determining if a subject is contraindicated from having this procedure. The following is a list of some common conditions that may preclude the subject from having MRI scans. However, this should not be used as a substitute for local clinical standards of care. The ultimate decision to perform the MRI rests with the site radiologist, the investigator, and the standard set by the local IRB/IEC:

- Subjects who have a history of claustrophobia.
- Subjects with a pacemaker, epicardial pacemaker wires, MRI-incompatible cardiac valve prostheses, and MRI-incompatible vascular clips less than 2 months old or MRIincompatible aneurysm clips of any age.
- Subjects with MRI-incompatible cochlear implants.
- Subjects with spinal nerve stimulators.
- Subjects with an infusion pump.
- Subjects with metallic fragments in the eyes/orbits or in the vicinity of the brain or major neurovascular structures of the body.
- Subjects with an employment history that involves exposure to welding, unless absence of metallic fragments is documented by X-ray examination as per institutional practice. Subjects who have shrapnel at any place in their body.

In lieu of an MRI, a CT scan may be substituted if subjects are unable to tolerate an MRI or an MRI is contraindicated for medical reasons. Any proposed CT scan must be discussed with and approved by the Medical Monitor on a case-by-case basis.

13.2 Adverse Events

13.2.1 Definitions

Adverse Event

An Adverse Event (AE) is any untoward medical occurrence in a participant or clinical investigation participant undergoing a study procedure or administration of a study drug. An AE can therefore be any unfavorable and unintended sign (including an abnormal laboratory finding), symptom, or disease temporally associated with the use of the study drug, whether considered related to the study drug or not.

Related Adverse Event

A related AE is an AE with a causality rating of "possible" or "probable".

Not related Adverse Event

A not related AE is an AE with a causality rating of "unlikely" or "unrelated".

Laboratory Abnormality

A laboratory abnormality is any clinically significant laboratory abnormality suggesting a disease or organ toxicity and which is of a severity requiring active management (i.e., changes of dose, discontinuation of drug, more frequent follow-up, medical treatment or a diagnostic investigation). Laboratory abnormalities are also considered AEs, if clinically significant.

Pretreatment Adverse Events

A pretreatment AE is any AE occurring during the pretreatment period (between informed consent and initiation of a study drug).

Post-study Adverse Event

A post-study AE is an AE occurring up to 30 days after the treatment period.

Treatment-emergent Adverse Events

Treatment-emergent adverse events (TEAEs) are all AEs occurring during the treatment period or a pretreatment AE that worsens in intensity during the treatment period.

Treatment Period

The treatment period is the period during which a participant receives study drug (i.e., first dose through last dose).

Serious Adverse Event

A serious adverse event (SAE) is any untoward medical occurrence that results in death, is life-threatening, requires in-participant hospitalization or prolongation of existing hospitalization, results in persistent or significant disability/incapacity, is a congenital anomaly/birth defect observed in any offspring of the participant conceived during treatment with the study drug or is an important medical event. See Section 14 for more details on SAEs.

13.2.2 Collection and Rating of Adverse Events

During the course of the study (i.e., from the signing of the ICF through the Follow-up Visit plus 30 days for any SAE) all AEs, irrespective of the relatedness to the study drug, will be collected and reported on the Adverse Event Report Form. The seriousness criteria should not be confused with the intensity of the event. In case of an SAE, a Serious Adverse Event Report Form must be completed and transmitted to the Sponsor or designee.

Overdoses and medication errors in the presence of clinical consequences should be recorded as AEs. The clinical consequence should be reported as "[enter AE] due to overdose".

13.2.2.1 Onset Date

The onset date is the date when the first sign(s) or symptom(s) were first noted. For example, if the AE is an abnormal laboratory test (such as "platelets low"), the onset date is the date when the sample was taken. If the participant was hospitalized for meningitis, and symptoms such as fever, headache and nausea started the day before the hospitalization, the onset date is the day symptoms presented versus day of hospitalization.

13.2.2.2 Assessment of Intensity

The intensity of each AE will be rated according to the following 3-point scale:

- Mild: Awareness of signs or symptoms, but no disruption of usual activity.
- Moderate: Event sufficient to affect usual activity (disturbing).
- Severe: Inability to work or perform usual activities (unacceptable).

13.2.2.3 Relationship to Study Drug

The causal relationship of the study drug to an AE will be rated according to the following 4-point scale:

- **Unrelated:** Clearly and incontrovertibly due only to extraneous causes and does not meet criteria listed under possible or probable.
- Unlikely: Does not follow a reasonable temporal sequence from administration; may have been produced by the participant's clinical state or by environmental factors or other therapies administered.
- Possible: Follows a reasonable temporal sequence from administration; may have been produced by the participant's clinical state or by environmental factors or other therapies administered.
- Probable: Clear temporal association with improvement on cessation of study drug or reduction in dose. Reappears upon re-challenge or follows a known pattern of response to the study drug.

13.2.2.4 Action Taken

The action taken toward the study drug in response to an AE will be listed as one of the following:

- None: No change in study drug dosage was made.
- Reduced: Dose of study drug was reduced.
- **Discontinued:** The study drug was permanently stopped.

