Serial monitoring of ALT/AST/bilirubin and INR will be performed, initially with repeat values within 4 days of discontinuation of study drug. If LFTs are still elevated 4 days post-study drug interruption, participants should have LFTs checked again 4 days later (+/- 1 day). The site investigator and Medical Monitor should agree to a plan for further LFT monitoring depending on whether the LFTs are still increasing or trending towards normal. Repeat testing should be carried out until LFTs have normalized. The LFTs in this instance can also be run locally for more rapid turnaround.

In the event a reversible etiology is found to explain the elevated liver enzymes (such as a common bile duct stone), drug may be restarted following normalization of LFTs, and after discussion between the Medical Monitor and site PI.

Study drug will be temporarily discontinued if a participant does not achieve the aforementioned levels of elevated transaminases but has an elevation of ALT or AST >3 X

ULN. These participants will have their liver function retested within 4 days after their last dose of study drug. If transaminases are still elevated 4 days post-study drug interruption, participants will have LFTs checked again 4 days later (+/- 1 day), and the site PI and Medical Monitor will agree to a plan for further monitoring of the findings. The LFTs in this instance can also be run locally for more rapid turnaround.

LFTs do not need to be intensively monitored when ALT and AST are ≤ 3 X ULN with no elevation of bilirubin, however the investigator and the Medical Monitor will formulate a plan for serial testing of LFTs. Cessation of dosing is not required in this circumstance but may be temporarily interrupted at the discretion of the investigator.

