10.3.1 Concomitant COVID-19 Treatment Restrictions

If a participant is treated for COVID-19 infection, the following recommendations would allow the participant to remain in the trial:

Administration of the COVID-19 antiviral treatment Paxlovid[™] (nirmatrelvir tablets, ritonavir tablets) will restrict concomitant administration of CT1812 because the ritonavir component is a potent CYP450 3A4 inhibitor. If a participant starts Paxlovid[™] treatment, CT1812 dosing will be held for a total of twelve days starting with Paxlovid[™] treatment initiation (Day 1). This time covers the five-day course of Paxlovid[™] administration and

seven days to allow for regeneration of CYP450 3A4. CT1812 dosing as per protocol requirements will resume after the 12-day hold (Day 13). If a participant is prescribed Lagevrio™ (molnupiravir), the preclinical data indicates it is neither metabolized by CYP isoenzymes, nor does it interact with them. Therefore, no cessation of CT1812 is required if Lagevrio™ is employed.

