#### 7.4. Exposure and Compliance

For all of the below formulas, i = individual participant for the entire treatment period.

• Total days of exposure will be calculated as:

$$\sum_{i}$$
 Days on Study Drug

• Study drug compliance will be calculated as:

$$\frac{\sum_{i} Actual \ Capsules \ Taken}{\sum_{i} Planned \ Capsules} \times 100$$

Compliance will be calculated using drug accountability data over the entire treatment period for each participant, up to treatment completion or discontinuation. Planned capsules will be calculated as 2 × the number of days between the first and last dose of study drug (inclusive).

Study drug exposure and compliance information will also be listed.

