#### 9.1.1. Adverse Events Leading to Withdrawal

A summary of incidence rates (frequencies and percentages) of TEAEs leading to treatment discontinuation, by treatment group, SOC, and PT will be provided for the Safety Population.

A data listing of AEs leading to study drug discontinuation will also be provided, displaying details of the event(s) captured on the CRF.

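### The adverse-event action list has no code for the temporary drug holds that the protocol requires, and the SAP compliance formula counts protocol-directed hold days as capsules not taken

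*Protocol*

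**What the plan says.** **Recording.** Protocol 13.2.2.4 presents the action list as closed: "The action taken toward the study drug in response to an AE will be listed as one of the following". The entries are None ("No change in study drug dosage was made"), Reduced ("Dose of study drug was reduced") and Discontinued ("The study drug was permanently stopped").

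**Holds.** Protocol 7.2.1 and the synopsis provide for temporary stops. For ALT or AST above 3 x ULN that does not meet the higher stopping levels, "Study drug will be temporarily discontinued if a participant does not achieve the aforementioned levels of elevated transaminases". Both places also allow a restart after a higher-level liver-test stop if a reversible cause is found, and interruption at the investigator's discretion at or below 3 x ULN. Protocol 10.3.1 covers Paxlovid: "CT1812 dosing will be held for a total of twelve days", with dosing resumed on Day 13.

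**Analysis.** SAP 9.1 counts participants with TEAEs leading to treatment discontinuation, and SAP 9.1.1 adds "A summary of incidence rates (frequencies and percentages) of TEAEs leading to treatment discontinuation" by treatment group, SOC and PT. Neither section has a row for interruption. SAP 7.4 defines compliance as capsules taken over capsules planned. Its denominator is: "Planned capsules will be calculated as 2 × the number of days between the first and last dose of study drug (inclusive"). It gives no rule for hold days, and does not say whether they count among the days on study drug.

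**The concern.** A site that holds and then restarts drug because of an adverse event has no accurate entry to choose. None says dosing did not change, Reduced says the dose was lowered, and Discontinued says the stop was permanent. The protocol's one common dose modification goes unnamed, while Reduced names a step for which I found no provision in a regimen of two capsules daily.

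Liver-test holds do reach the AE form. Protocol 13.2.1 treats clinically significant laboratory abnormalities as AEs and cites changes of dose and stopping of drug as examples of the management involved. The gap also touches causality: the definition of a probable relationship in 13.2.2.3 turns on improvement after cessation and recurrence on re-challenge, which is the kind of information that a hold and restart produces.

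At stake is the account of tolerability by arm. Interruptions would go uncounted, and some could appear among discontinuations. The compliance summary would also show participants who did what the protocol told them to do as having missed doses.

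**Working it through.** **1. Each hold provision against the action list**

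| Situation | Nature of the stop | Code that fits |
|---|---|---|
| ALT or AST >3 x ULN, below the higher stopping levels (Protocol 7.2.1) | Required, temporary | None of the three |
| Higher-level liver-test stop, reversible cause found (7.2.1) | Restart allowed | Discontinued, until dosing resumes; then none |
| ALT and AST at or below 3 x ULN (7.2.1) | Discretionary interruption | None of the three |
| Paxlovid (10.3.1) | Required, 12 days | None of the three, if entered as the action for a COVID-19 AE |

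The last row is the weakest. That hold is triggered by a concomitant medication, and the action field concerns responses to an AE. It matters mainly for compliance.

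**2. Compliance under SAP 7.4**

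The plan states no compliance figure or threshold, so there is none to reproduce. Inputs:
- 2 capsules a day (Protocol 7.2) for 182 days (Protocol 4.4), so planned capsules = 2 x 182 = 364.
- Paxlovid hold h = 12 days (Protocol 10.3.1).
- Liver-test hold: length not fixed. Protocol 7.2.1 sets a retest within 4 days and, if values are still raised, another 4 days later (+/- 1 day). I assume h = 4, 8 or 9 days; a real hold could be longer.
- Every capsule outside the hold is taken, and dosing restarts.

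Compliance = 100 x 2(182 - h) / 364.

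| Hold | Taken / planned | SAP 7.4 | Hold days excluded |
|---|---|---|---|
| 4 days (assumed) | 356/364 | 97.8% | 356/356 = 100% |
| 8 days (assumed) | 348/364 | 95.6% | 348/348 = 100% |
| 9 days (assumed) | 346/364 | 95.1% | 346/346 = 100% |
| 12 days (Paxlovid) | 340/364 | 93.4% | 340/340 = 100% |

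Two boundary cases:
- The effect grows when exposure is short. With a last dose on Day 60 and a 12-day hold before it, compliance is (60 - 12)/60 = 80.0%.
- It vanishes if dosing never restarts, because the last dose then precedes the hold. With a last dose on Day 99, compliance is 198/198 = 100%.

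Exposure has the same ambiguity. A 12-day hold gives 182 days or 182 - 12 = 170 days on study drug, depending on a convention that the SAP does not state.

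**The case against.** Several points on the other side stand.

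- **A reader might infer that holds will be coded as permanent discontinuation and so inflate the discontinuation table.** The documents do not show this. SAP 9.1 and 9.1.1 name no source field for that table. Protocol 9.5.1 has the date and reason for study drug discontinuation recorded on the CRF separately. The wording of the Discontinued code steers sites away from using it for a hold. If sites choose None, the discontinuation table is right and only the interruptions are lost. One wrongly coded participant in an arm of 48 would move the rate by 1/48 = 2.1 points, but that requires coding against a written definition. The eCRF may also carry a further option.
- **A reader might infer that the distortion falls on the 300 mg arm.** The support is thin. Protocol 4.3 reports one participant with ALT at 4.7 x ULN, at 560 mg, in a study of 19, and itself says the numbers do not permit definitive conclusions on AEs by dose. Among the four healthy volunteers with smaller liver-test rises, one was on placebo. Nothing ties Paxlovid use to dose.
- **The liver signal is not hidden.** SAP 9.2.1 tabulates ALT and AST at or above 3 x ULN whatever action code is used. What was done with the drug in response is still missing.
- **Compliance drives nothing.** The SAP sets no threshold, and the Per-Protocol Population has been removed. Capsules taken over the dosing span is also a legitimate measure of dosing received. It does not measure adherence to protocol-directed dosing, and the SAP does not say which is meant.

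**Conclusion.** The point holds as a reporting defect in two parts.

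First, the action list and the hold provisions do not fit together. AE-driven interruptions cannot be recorded accurately from the protocol's list, and the SAP plans no summary of them by arm. This rests on the protocol text alone, because the eCRF was not available.

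Second, SAP 7.4 understates compliance, relative to protocol-directed dosing, for any participant who restarts after a hold. The shortfall is 6.6 percentage points for one Paxlovid hold over full treatment, and 2.2 to 4.9 points for an assumed liver-test hold of 4 to 9 days. These figures assume perfect adherence outside the hold.

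The consequence is confined to descriptive safety and exposure tables. No analysis population, efficacy test or estimate changes. The documents establish neither that sites have miscoded holds nor that the arms would be affected unequally. The correction is still worth making, because tolerability is part of the primary objective and the repair is small.

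**What to change.** - **Protocol 13.2.2.4 and the eCRF:** reconcile the action list with the hold provisions by adding an Interrupted category, meaning temporarily stopped. If the eCRF already has one, align the protocol text with it.
- **SAP 9.1 and 9.1.1:** keep the discontinuation rows for permanent stops, name the field they are drawn from, and add TEAEs leading to treatment interruption by arm.
- **SAP 7.4:** exclude documented protocol-directed hold days from planned capsules and from days on study drug, or report compliance both ways. Tabulate hold days by arm and reason.

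The cost is one eCRF option, one set of table rows and a revised denominator. The real burden is retrospective. Protocol version 6.0 is dated June 2023 and SAP version 2.0 May 2024, so many events may already have been entered. The documents describe accountability by capsule count, not by daily dosing dates, so hold start and stop dates may need site queries. No change to the clinical hold rules is proposed.

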13.2.2.5 Outcome of Adverse Event

The outcome of an AE will be recorded as one of the following:

- Recovered: Fully recovered or the condition has returned to the level observed at baseline.
- Recovered with sequelae: Resulted in persistent or significant disability or incapacity; the nature of the sequelae should be specified.
- Not recovered

Death

13.2.3 Adverse Event Follow-up

Adverse events requiring therapy must be treated with recognized standards of medical care to protect the health and well-being of the participant.

Any participant who has any AE (whether serious or non-serious) or clinically significant (in the Investigator's opinion) abnormal laboratory test values will be evaluated by the Investigator or a monitoring physician and will be treated and followed up until the symptoms or values return to normal or acceptable levels, as judged by the Investigator and the Sponsor.

Adverse events that are unresolved at end of study or upon early withdrawal will be tracked at least weekly by site staff until resolution, for 30 days, or until the participant is lost to follow-up (defined as failure to respond to three phone messages left on separate days and one certified letter requesting follow-up).

Participants will be instructed to inform site staff of any AEs occurring during the 30-day period after discharge or early withdrawal.

Any follow-up information available at the time of the participant's end of study will be included in the clinical study report.

Any SAE that is considered to be unexpected and related to the study drug occurring after the end of study should be forwarded to the Sponsor. These cases will be handled and submitted as expedited reports but will not be included in the clinical study report.

Note: Any SAE will be reported to NIH by the sponsor within 48 hours of the time when the Sponsor becomes aware of the event

14 Serious And Other Significant Adverse Events

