5 STUDY OBJECTIVES

5.1 Primary Objectives

• To assess the safety and tolerability of CT1812 in participants with mild to moderate Alzheimer's disease.

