9.5 Participant Withdrawal Procedures

9.5.1 Follow-up Procedures for Participants Who Withdraw Prematurely

The date and the reason for study drug discontinuation or participant withdrawal from the study must be recorded on the Case Report Form. If the participant has received one or more doses of clinical trial material, and has not withdrawn consent, the participant shall return for the End of Study (EOS) visit. The EOS visit for early terminations will occur within 2 weeks of the last dose.

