14.1.2 Serious Adverse Event Reporting by the Investigator to the Sponsor

Any SAE that occurs after a participant has entered the study, whether related to study drug or not, must be reported to the CRO immediately (within 24 hours) via e-mail at the address noted below. A completed Serious Adverse Event Report Form with as much detail as possible must be included with the email. The Investigator must report all SAEs occurring from the time the participant signs the ICF until 30 days after last treatment with the study drug.

Sponsor Representative and Contact Information for SAE Reporting:

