#### 9.1.2. Deaths and Serious Adverse Events

Any deaths that occur during the study will be listed.

Serious adverse events will be listed and also tabulated by SOC and PT and presented by treatment.

[figure not shown]

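### Protocol 13.2.3 bars from the clinical study report some unexpected, drug-related SAEs that fall inside the required collection window, while the SAP would count them

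*Protocol*

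**What the plan says.** The primary objective in Protocol 5.1 is safety: "To assess the safety and tolerability of CT1812 in participants with mild to moderate Alzheimer's disease". These places decide which SAEs reach the report:

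- **Protocol 13.2.3** directs that any SAE "considered to be unexpected and related to the study drug occurring after the end of study should be forwarded to the Sponsor", and then adds: "These cases will be handled and submitted as expedited reports but will not be included in the clinical study report".
- **Protocol 13.2.2** sets the collection period: "from the signing of the ICF through the Follow-up Visit plus 30 days for any SAE".
- **Protocol 14.1.2** sets a different end: "The Investigator must report all SAEs occurring from the time the participant signs the ICF until 30 days after last treatment with the study drug".
- **Protocol 9.5.1**, on participants who stop early: "The EOS visit for early terminations will occur within 2 weeks of the last dose".
- **SAP 9.1.2**: "Serious adverse events will be listed and also tabulated by SOC and PT and presented by treatment". SAP 6.1.8 and 9.1 define a treatment-emergent AE by its start only, with no closing date. SAP 10, which lists departures from the protocol, does not mention the 13.2.3 rule.

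The term *end of study* is used in more than one way. The only formal definition (Protocol synopsis, repeated in SAP 3.1) is for the trial as a whole: the final visit or procedure of the final participant. Section 13.2.3, just before the disputed passage, speaks of an individual participant's end of study. Protocol 9.5.1 gives the name End of Study visit to the early-termination visit, and SAP 6.1.6 uses the EOS label for Day 182.

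**The concern.** The protocol asks sites to gather these SAEs and then tells the report's author to leave some of them out. The SAP gives the opposite instruction for the same event. Because safety is the primary objective, whether a related, unexpected SAE is counted should not depend on which document the author follows, especially if that choice is made after unblinding. SAP 9.1 reports participants with any treatment-related SAE. With few such events expected, a single omission would show in that row.

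**Working it through.** **1. The plan's own safety figure.** Protocol 15.2 and SAP 3.2 give 48 participants per dose, a 5% true prevalence and a 91% chance of seeing at least one drug-related AE. Check: 1 − (1 − 0.05)^48 = 0.9147, or 91.5%. The figure reproduces. The documents give no figure for the exclusion itself.

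**2. Where the windows end for a completer.** Last dose is Day 182 and the follow-up visit is Day 210 ± 2.

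- 14.1.2: 182 + 30 = Day 212.
- 13.2.2: 210 + 30 = Day 240 (nominal).

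For an early terminator, 14.1.2 ends 30 days after the last dose. The end under 13.2.2 is unclear, because 9.5.1 provides an EOS visit but no separate Follow-up Visit.

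**3. Days inside a required window but after end of study.**

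| Meaning of end of study | Left under 14.1.2 | Left under 13.2.2 |
|---|---|---|
| Participant level, completer at Day 210 ± 2 | 212 − 212 = 0 to 212 − 208 = 4 (2 nominal) | 30 |
| Participant level, early terminator, EOS visit 0 to 14 days after last dose | 30 − 14 = 16 to 30 − 0 = 30 | 30, if that visit stands in for the Follow-up Visit |
| Day 182 as EOS (SAP 6.1.6 label), completer | 212 − 182 = 30 | 240 − 182 = 58 |
| Trial level (synopsis) | only windows still open at the last participant's last visit | never empty: the last participant's own window runs on for 30 days |

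Under both the participant-level and the trial-level meaning, 13.2.2 leaves some days on which an SAE must be collected but can be barred from the report.

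**4. Size, participant level, 14.1.2 window.** Assumptions: constant hazard; 15% early terminators (a planning figure taken from the ADAS-Cog calculation); last dose on Day T between 30 and 150; EOS visit L = 0 to 14 days later. The share of qualifying events after end of study is

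f = [0.85 × 2 + 0.15 × (30 − L)] / [0.85 × 212 + 0.15 × (T + 30)].

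- T = 30, L = 0: (1.7 + 4.5) / (180.2 + 9.0) = 3.3%.
- T = 150, L = 14: (1.7 + 2.4) / (180.2 + 27.0) = 2.0%.

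Applied to the plan's detection figure, 1 − [1 − 0.05(1 − f)]^48 gives 90.7% to 91.0%, against 91.5% with no exclusion. This overstates the effect, since only AEs that are also serious and unexpected are barred.

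Within an early terminator's own window the share is (30 − L)/(T + 30): 16/180 = 9% to 30/60 = 50%. For a completer it is 2/212, about 1%.

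**5. Size, participant level, 13.2.2 window, completer.** 30/240 = 12.5% of days, and the detection figure becomes 1 − (1 − 0.05 × 0.875)^48 = 88.3%. Those days lie 28 to 58 days after the last dose (210 − 182 and 240 − 182), where a constant hazard for drug-related events is probably generous.

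**6. Size, trial level.** If k of 144 participants still have an open window at the last participant's last visit, at most k × 30/(144 × 240) of collected person-days are affected: 0.1% for k = 1 and 0.9% for k = 10. The values of k are assumed.

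**7. One event, as illustration only.** One related SAE among 2 × 48 = 96 CT1812 participants is 1/96 = 1.0%. Omitted, it is 0%.

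**The case against.** The best defence is that 13.2.3 concerns only late events. The parenthesis in 13.2.2 describes the course of the study as running through the extra 30 days. If end of study meant the close of that period, nothing inside the window would be barred. But 13.2.3 itself treats end of study as a point from which unresolved AEs are tracked for up to 30 days, and the synopsis places it at a visit or procedure. That defence is strained, and it shows at least that the sentence needs clarifying.

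Three further objections stand and limit the point.

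- **Early terminators.** A reader might infer that the rule falls hardest on those who stop early. That needs the participant-level meaning, the EOS visit as end of study, and the 14.1.2 window. Section 13.2.3 names early withdrawal separately from end of study. Under the synopsis definition, most early terminators would be unaffected.
- **Selection on causality.** A reader might infer that drug-related SAEs are removed while unrelated or expected ones on the same day stay in. The text supports this only in part: it bars the first kind from the report and is silent on the second.
- **The planned tables.** The SAP does not implement the exclusion. As written, its outputs would count any such SAE that is in the database.

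**Conclusion.** The conflict is real. For an unexpected, related SAE with onset inside the required window but after end of study, 13.2.3 says to leave it out of the report, and the SAP says to list and tabulate it. This holds under both the participant-level and the trial-level meaning.

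The expected number of events is small. The assumed scenarios give about 2.0% to 3.3% of qualifying events (participant level, 14.1.2 window) and 0.1% to 0.9% of person-days (trial level). The highest figure worked here for a completer ending at Day 210 is 12.5% of days, under the 13.2.2 window. All rest on constant hazard or on assumed counts, and the documents give no expected event rate.

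The documents do not establish a material downward bias in the SAE rate, nor a particular loss among early terminators. The case for change rests on contradictory instructions for the primary objective and on how little the correction costs.

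**What to change.** - **Protocol 13.2.3:** replace the exclusion. Every SAE with onset inside the collection window is entered in the database, counted in the SAE and TEAE tables and included in the clinical study report, whatever its causality or expectedness and whether or not the participant's last visit has passed. Handling by expedited report alone applies only to SAEs with onset after that window.
- **Define end of study** for 13.2.3, at participant or trial level.
- **Reconcile the window ends** in 13.2.2 and 14.1.2, and say what the end date is for early terminators.
- **SAP 9.1.2:** state the same inclusion rule. Make clear that the SAP's TEAE definition governs the tables, because the one in Protocol 13.2.1 closes at the last dose.

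Cost: a few sentences, possibly a few more narratives, and an SAE count that may be slightly less favourable.
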